## **Statistical analysis**

**Part A:** Descriptive statistics will be performed. Results will be expressed as absolute numbers and percentages, mean  $\pm$  standard deviation (SD) or median (minimum; maximum) depending on the variable types and distributions, separately for the prospective and the retrospective dataset.

For the prospective study, multivariate logistic regression will be performed to identify risk factors associated with specific PN prescription: for example, inadequate administration of PN. In addition, data from the prospective study and the retrospective chart review will be compared by unpaired t-test, Mann-Whitney-test or chi-square test as appropriate. A p value  $<0.05$  will be considered statistically significant. **Part**

**B:** For the Intralipid and the ClinOleic analysis, all variables will be tested for normal distribution (Shapiro Wilks test). *Primary outcome* is length of stay (in days). The Intralipid and ClinOleic groups will initially be compared with unpaired t-test or Mann-Whitney test as appropriate. *Secondary outcomes*: other clinical outcomes (days in ICU, antibiotic-days, infections, mortality) will also be analyzed the same way initially. For secondary outcomes that may change over time, i.e. hs-CRP, pre-albumin and other laboratory results, BMI, arm circumference, hand grip strength, changes will be compared between groups using unpaired t-test or Mann-Whitney test as appropriate. To account for possible covariate effects (eg. age, baseline BMI, Charlson comorbidity index), regression methods such as generalized linear models will be employed. All tests will be based on two-sided alternatives and a test will be considered statistically significant using alpha=0.05. SAS Enterprise Guide 4.1 software (SAS Institute Inc., Cary, NC, USA) will be used.

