## **Background**

In a prospective quality control study in Switzerland, 200 patients receiving PN were evaluated to see if PN prescription was justified according to the 2002 ASPEN guidelines. They were recruited during 18 weeks from Medicine, Surgery and Intensive Care Units. In this study, the Nutrition Support Team did not interfere with the PN prescriptions which were made by the medical staff of the different wards. They concluded that PN prescription was justified in all but 14 patients (7%). The energy supply was adequate only in 31.5% of the patients and overfeeding was more frequently observed. Women, thin and elderly patients were at more risk for overfeeding. The same happened with the protein supply, only 21% of the patients received an adequate supply and 65.5% received excess proteins. Also, 23.5% of the patients did not receive supplementation of vitamins and/or trace elements in their PN(18). This study shows the need to establish nutrition support protocols, particularly for PN.

In one Canadian study (19), the authors conducted a cross-sectional national survey of dietitians working in ICUs and identified interventions to target for quality improvement initiatives. In this study, 24% of the sites that responded reported the presence of a nutrition support team. The enteral route was the main route of administering nutrition support and of the 702 patients studied, 7.1% received parenteral nutrition only. Underfeeding seemed

to be a significant problem in the group of patients that stayed in the ICU for more than 3 days since 16% of these patients did not receive any nutrition support. Furthermore, of those that received nutrition support the average of calories and proteins received was 56% to 62% of their estimated needs over the first 12 days in the ICU. Another study conducted in Canadian ICUs evaluated whether an auditing practice and providing feedback is an effective strategy to improve adherence to nutrition guidelines. Twenty-six ICUs participated in an audit in 2007 and were given a feedback of their performance compared with the Canadian Critical Care Nutrition guidelines. The authors observed improvement in some nutrition practices in many ICUs after the reaudit in 2008 (20).

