### **Study design**

This is a prospective study that will evaluate the indications of parenteral nutrition in an inpatient setting. As part of their PN prescription, patients will receive either standard lipid (Intralipid) or OO-based lipid emulsion (ClinOleic), alternately depending on their time point of PN start, i.e. one person will receive Intralipid, the next one ClinOleic, etc. We will collect information from patients that have started with parenteral nutrition during their hospitalization and that are hospitalized in medical, surgical or ICU wards. We will also collect retrospective data of 100 patients to compare if the actions of the nutrition team and results change with respect to the prospective data.

Inclusion Criteria:

- Patients 18 years or older

- Patients that are expected to require PN for 5 days or more during their hospitalization
- Patients hospitalized in medical, surgical or ICU wards
- Signed informed consent either from the patient, their legally authorized representative or a direct family member

Exclusion Criteria:

- Patients without PN during their hospitalization

**Part A:** Patients will be approached when they start with PN during their hospitalization and will be followed until their last day of PN or, if occurred before PN ends, death. **Part**

**B:** For the proposed study, we will start PN as usual, according to the patients needs. We will randomly assign patients to receive either Intralipid or ClinOleic as the lipid emulsion in the PN. The amount of calories from the lipid emulsion will be equivalent.

Patients will be followed for one week after their last day on PN and, in addition, major outcomes such as mortality and length of stay will be assessed during the entire hospitalization.

Information regarding the patients nutrition will be obtained from the hospital chart and by direct communication with the PN team (dietitian, nurse, pharmacist) after signed informed consent.

We will analyze the nutritional indications and laboratory results of patients hospitalized in different units who are starting with PN alone or in combination with enteral or oral feeding twice a week. We will use a registry to enter the data.

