Measurements: :**Part A** 1) Patient demography: age, sex; 2) Type of patient: medical, surgical and/or ICU patients; 3) Type of any surgery the patient has during hospitalization; 4) Primary indications related to parenteral nutrition, comorbidities, updated CCI (31,32); 5) Nutritional assessment: weight, height, BMI, SGA, estimated energy and protein requirements; 6) comparison of energy received as a goal vs calculated energy requirements using published equations; 7) Energy, dextrose, aminoacids and lipids received by PN.

Total energy and proteins received including enteral nutrition and oral intake. Energy provided by Propofol, if received. In case of enteral nutrition, name and amount of product used; 8) Type of line used (peripheral or central); 9) Vascular access; 10) Reason for ending PN; 11) Number of times and reasons for interruption of PN; 12) Weekly PN related laboratory results; 13) Complications secondary to PN; 14) Outcome of patient

**Part B:** We will include the same measurements as in part A, but will add some additional nutritional parameters which will be done at baseline (Day 0) and after 10 days (Day 10)

with PN. Baseline or day 0 assessments to be done prior to or within 24 hours of PN initiation. Day 10 measurements to be done on day 10 of PN administration. If the PN ends before day 10, we will consider a cutoff at day 7 of PN. This means that if the PN ends before day 7, we will not repeat the measurements or blood work. If PN ends between days 7-9 we will repeat the measurements instead of doing them on day 10 for this special cases.

The parameters to measure will be: hand grip strength (kg), mid arm circumference (cm), SGA and weight as measures of nutritional status. We will also add hs-CRP, pre-albumin, and fatty acid profile in red blood cells (RBC) and plasma to the laboratory results at both time points. Clinical outcomes (documented infections, antibiotic-days or other adverse events) will be monitored for one week post-PN. In addition, mortality and length of stay will be documented for the entire hospitalization.

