## **Feasibility and Sample Size**

**Part A:** Based on previous studies, there are about 200 in-patients per year receiving PN. All patients will be assessed as per standard medical guidelines for PN and it is expected that 90% will agree to participate in the project. We calculate that we will have enrolled about 50 patients for Part A, before we start with part B. We will later include 150 more patients from Part B to have a total of 200 patients. We will compare the data obtained with 100 retrospective patients to see if the actions of the nutrition team changed since we started the project.

**Part B:** When we receive the ClinOleic in the hospital, patients will receive either SO-based lipid emulsion (Intralipid= 150 patients) or OO-based lipid emulsion (ClinOleic=150 patients) on an alternate basis (one-to-one) for the duration of the PN.

The total number of patients including part A and part B is estimated to be 350 patients. It is expected to take about one and a half years to recruit this number of patients.

For the Intralipid and ClinOleic analysis, we based our sample size on a study that evaluated the use of either SO or SO + fish oil (FO) in 206 patients with gastrointestinal or colonic cancer during 7 days after surgery and found that the patients that were given the FO treatment had significantly shorter length of stay than the SO group (Mean (SD) 15(5) versus 17(8) p= 0.041). Also, they had fewer infectious complications (50). Another study compared soybean oil and soybean oil+FO in 57 elderly patients with colorectal cancer. In the treatment group, there were fewer infectious complications and incidences of systemic inflammatory response syndrome (SIRS), and shorter lengths of hospital stay were observed(51).

Based on this, we estimate that a sample size of 150 in each group with a power of 0.8 and alpha of 0.05 will be sufficient to show a similar difference in length of stay between the two groups (soybean or ClinOleic) using the online sample size calculation provided by G.W. Snedecor & W.G. Cochran  
<http://www.biomath.info/power/ttest.htm>.

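### Part A's comparison of prospective patients with 100 charts is unadjusted and the chart selection is not clearly defined, so a case-mix difference could mimic or mask a change in practice

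*Combined protocol and SAP*

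**What the plan says.** Study design announces the collection of "retrospective data of 100 patients to compare if the actions of the nutrition team and results change with respect to the prospective data". Feasibility and Sample Size repeats the purpose: the 100 charts serve "to see if the actions of the nutrition team changed since we started the project". The same section counts the prospective Part A patients as 50 + 150 = 200.

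For the test itself, Statistical analysis, Part A says that "data from the prospective study and the retrospective chart review will be compared by unpaired t-test, Mann-Whitney-test or chi-square test as appropriate", with significance at p < 0.05. Descriptive results are given "separately for the prospective and the retrospective dataset". The one Part A regression is confined to the prospective study and looks for risk factors. The sentence on covariate effects (age, baseline BMI, Charlson index) stands in the Part B paragraph and follows the lipid-group comparisons.

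Among the inclusion criteria in Study design are signed consent and "Patients that are expected to require PN for 5 days or more during their hospitalization". For the charts, the plan gives the number and the purpose. It gives no calendar period and no sampling method, and does not say which criteria apply. The Part A measurements already include age, sex, BMI, Charlson index and "Type of patient: medical, surgical and/or ICU patients".

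**The concern.** The comparison is given a before-and-after reading: a significant difference is to count as a change in what the team does. That reading is safe only if the two sets of patients are alike in whatever else drives the prescription items. Two features of the plan make this uncertain. Consent and a forward-looking estimate of PN duration cannot be applied directly to a chart. Nor is it stated whether the charts are consecutive, random or chosen in some other way.

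The plan's own Background gives a reason to expect case mix to matter. The 200-patient Swiss audit it cites found overfeeding more likely in women, thin patients and the elderly. A shift in sex, BMI or age between charts and prospective patients could therefore move the adequacy rates while the team behaves exactly as before, or offset a real improvement.

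**Working it through.** The plan gives no power or effect size for this comparison, so there is no figure to reproduce.

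**Inputs.** Group sizes are 200 and 100 (Feasibility and Sample Size). Base rates come from the Swiss audit in Background: "The energy supply was adequate only in 31.5% of the patients and overfeeding was more frequently observed", and for protein "only 21% of the patients received an adequate supply and 65.5% received excess proteins". Inadequacy is then 100 − 31.5 = 68.5% (energy) and 100 − 21 = 79% (protein). In that audit ward staff prescribed without the nutrition team, so rates here may differ. The test is taken as two-sided at 5%.

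**Standard error with equal rates.**
- Energy: √[0.685 × 0.315 × (1/200 + 1/100)] = 0.0569.
- Protein: √[0.79 × 0.21 × 0.015] = 0.0499.

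**Fall in inadequacy needed for 80% power.** Solve d = 1.96 × SE₀ + 0.84 × SE₁, with SE₀ from the pooled rate and SE₁ from the separate rates; charts are at the base rate.
- Energy, 68.5% to 51.7%: pooled rate 57.3%, SE₀ = 0.0606, SE₁ = 0.0584, d = 0.168.
- Protein, 79% to 63.4%: pooled rate 68.6%, SE₀ = 0.0568, SE₁ = 0.0531, d = 0.156.

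**Bias that distorts the test.** With a case-mix bias b and no true change, the rejection rate is Φ(−1.96 + b/SE) + Φ(−1.96 − b/SE).
- It reaches 10% at b = 3.7 points (energy) or 3.3 points (protein).
- It reaches 20% at 6.3 or 5.6 points.

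**What could produce such a bias.** For one two-level factor, b = (gap in its share between periods) × (gap in inadequacy between its levels). ICU versus ward is used as the example. All gaps are assumptions. Energy, SE 0.0569:

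| Share gap × inadequacy gap | b | Rejection rate |
|---|---|---|
| 10 × 10 points | 1 point | about 5.4% |
| 20 × 20 points | 4 points | 10.8% |
| 30 × 30 points | 9 points | about 35% |

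**Does adjustment help?** Simulation: 10,000 runs, 200 versus 100, logistic model with period, age, sex, BMI, three-level patient type and Charlson index (7 slopes).
- No true change; ICU share 50% prospective and 30% in charts; inadequacy 78.5% in ICU and 58.5% on the ward: rejection 10.8% unadjusted, 5.0% adjusted.
- True fall of 15 points with the same ICU shares; chart rates 82.5% and 62.5%. Charts: 0.3 × 82.5 + 0.7 × 62.5 = 68.5%. Prospective: 0.5 × 67.5 + 0.5 × 47.5 = 57.5%. The expected unadjusted fall is only 11 points. Power is 47% unadjusted and 71% adjusted.
- No imbalance: the SD of the estimate goes from 5.69 to 5.76 points, about 1% wider.

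**Can the data carry the model?** Patients in the rarer category among 300, per slope: energy 0.315 × 300 / 7 = 13.5; protein 0.21 × 300 / 7 = 9.0. For an item as rare as unjustified PN in the same audit (7%), it is 21 / 7 = 3.0, too thin for the full model.

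**Cost of missing chart covariates.** If 20% or 30% of charts (assumed) drop out, the energy SE becomes √[0.685 × 0.315 × (1/200 + 1/80)] = 0.0614 or, with 1/70, 0.0645. That is 8% or 13% above 0.0569.

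**The case against.** The strongest reply is that this is an audit comparison outside the listed Part A objectives, and that every bias figure above needs an assumed imbalance. Both statements are true. They limit the weight of the point but do not remove it, because the plan attaches a significance threshold and a conclusion about the team to the comparison.

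Second, case mix is partly handled already. Energy requirements are individualised (Penn State for ventilated ICU patients, weight-based otherwise, ideal body weight in obesity or ascites), so adequacy is partly scaled for ward and body size. Results are also shown by dataset, so imbalance in recorded characteristics can be seen. This stands in part, but seeing an imbalance does not correct the test.

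Third, the sentence on the charts directly precedes the inclusion criteria, which are not expressly limited to prospective patients. A reader might infer from the present point that the charts fall under different criteria. The documents do not show that; the age, ward and PN criteria can be read as covering both. What stands is ambiguity, plus two criteria that cannot transfer directly.

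Fourth, adjustment has costs. Patient type and BMI may partly reflect whom the team starts on PN, so for items about that choice adjustment could remove part of the change being audited. Chart covariates will be incomplete; the objectives already treat admission weight as available only where the chart records it. Both objections stand and shape the fix.

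A reader might also see bias in the fact that the plan does not say which 150 of the 300 Part B patients join Part A. That is missing detail; nothing shows that it distorts the prescription items.

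**Conclusion.** The point holds as a gap in the analysis plan: a non-randomised comparison with a stated before-and-after purpose has only unadjusted tests, and the chart selection is not clearly defined. It is a cheap improvement worth making, with medium confidence.

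It would go too far to infer that the comparison is biased, or that its false-positive rate is 11%. That rate belongs to one assumed scenario (20 × 20 points), and the audit rates behind it may not transfer to this hospital. Nor does the lipid comparison on length of stay suffer. The 200-versus-100 design can detect only fairly large falls in inadequacy (about 16.8 points for energy, 15.6 for protein), so a bias of a few points is not trivial beside what the comparison can show.

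**What to change.** In Statistical analysis, Part A:

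- For the key adequacy items (energy and protein received versus required), pre-specify a regression on period adjusted for age, sex, BMI, patient type and Charlson index, logistic for binary and linear for continuous items. State how patients in more than one type are coded.
- Report it beside the planned unadjusted tests, and base any conclusion that practice changed on the adjusted estimate.
- For sparse binary items use fewer covariates or a penalised (Firth) model.
- For items about who is started on PN, treat the adjusted result as a sensitivity analysis.

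In Study design:

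- Take the 100 charts consecutively from a stated period, under the same age, ward and PN-duration criteria as far as charts allow.
- Report missing covariates by period and say how they are handled.

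The chart rule must be fixed before extraction, because later analysis cannot repair an arbitrary sample.

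Cost: five covariates extracted from 100 charts and no new patients. Precision loss is about 1% with complete data, or about 8–13% if 20–30% of charts (assumed) are lost. Adjustment cannot remove time trends unrelated to the team, selection by consent (90% expected to agree) or differences between chart and prospective data capture. These limits should be stated with the result.

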#### **Part A:**

#### **Primary Objective**

- To evaluate parenteral nutrition prescriptions in hospitalized patients
- **Secondary Objectives**
- Describe patient population according to the pathology that caused the hospitalization
- Record the indication that determined the need for PN and whether they are medical, surgical or ICU patients
- Assess updated Charlson co-morbidity index (CCI)
- Record the number of days with intakes less than 50% of requirements or NPO before PN was prescribed
- Perform a nutritional assessment which includes: weight at admission (if recorded in chart) and at time of starting PN, height, body mass index (BMI), Subjective Global Assessment (SGA), albumin and estimate of nutritional requirements.
- Record the initial PN prescription in terms of energy and proteins
- Record how many days it took to reach the nutritional requirements estimated by the dietitian
- Compare energy received as a goal with calculated energy requirements using published equations
- Record the number of times PN was interrupted
- Record the total number of PN days the patient received
- Determine the type of line (central or peripheral) and number of days with peripheral and/or central lines.

- Determine the type of vascular access (if central line)
- Record laboratory results once a week to assess potential metabolic complications associated with PN
- Record catheter related infections, whether suspected or confirmed
- Record any other complications deemed related to PN
- Record number of antibiotic-days to treat catheter-associated infections
- Record the reason why PN was discontinued
- Record total length of stay
- Record in-hospital mortality and cause of mortality during PN as well as during entire hospital stay

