## **Part B: Intralipid vs ClinOleic**

### **Primary Objective**

To evaluate metabolic, nutritional, infectious and inflammatory parameters in patients receiving SO-based lipid emulsion compared to those of patients receiving OO -based lipid emulsion.

- Primary Outcome: length of stay
- Secondary Outcomes: mortality, nutritional parameters (anthropometry, handgrip-strength, mid-arm circumference, , pre-albumin), inflammation (high sensitivity C-reactive protein; hs-CRP), documented infections, ICU stay, antibiotic-days, liver enzymes, essential fatty acid status

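### The plan does not say how a stay that ends in death enters the primary length-of-stay test, so the test can favour the group with more or earlier deaths

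*Combined protocol and SAP*

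**What the plan says.** Under Part B, the outcome list gives "Primary Outcome: length of stay". Mortality, ICU stay, antibiotic-days and documented infections are secondary. The eligible population is "Patients hospitalized in medical, surgical or ICU wards".

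Follow-up for both stay and death runs to the end of the admission. Study design says "major outcomes such as mortality and length of stay will be assessed during the entire hospitalization", and the Part B measurements repeat that "mortality and length of stay will be documented for the entire hospitalization".

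Death is recorded. The Part A objectives include "Record total length of stay" and "Record in-hospital mortality and cause of mortality during PN as well as during entire hospital stay". The Part A measurements end with the patient's outcome, and Part B takes over all Part A measurements.

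For the primary analysis, the Statistical analysis section says "The Intralipid and ClinOleic groups will initially be compared with unpaired t-test or Mann-Whitney test as appropriate". For the secondary outcomes it says "other clinical outcomes (days in ICU, antibiotic-days, infections, mortality) will also be analyzed the same way initially". Generalized linear models then adjust for covariates, with age, baseline BMI and the Charlson index as examples.

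No section defines the primary outcome as time to live discharge, ranks or censors deaths, treats death as a competing event, or plans a sensitivity analysis for it.

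**The concern.** The trial reads a shorter stay as benefit: Feasibility and Sample Size takes its planning difference from a study in which the treated group went home sooner. A stay can also end in death. With total days as the only input, a death on day 6 scores better than a recovery on day 17. If decedents' stays are shorter than survivors', the primary result is pulled towards the lipid with more deaths or earlier deaths.

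Covariate adjustment does not remove this, because age, BMI and comorbidity do not say how a stay ended. A separate mortality comparison may alert the reader but does not alter the primary test.

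**Working it through.** **The plan's own figure.** Inputs from Feasibility and Sample Size: means 15 and 17 days, SDs 5 and 8, two-sided alpha 0.05, power 0.80, 150 per group. The mean variance is (25 + 64)/2 = 44.5, so SD = 6.67. Then n = 2 × (1.960 + 0.842)² × 44.5 / 2² ≈ 175 per group, and power at 150 is about 74%. The stated 150 is not reproduced. That is a separate matter; nothing below depends on it.

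**Direction of the bias.** Let survivors average s days in both groups. Let p be the death proportion and d the decedents' mean stay, with group A having more or earlier deaths. The difference in mean total stay is

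A − B = pA(dA − s) − pB(dB − s).

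Take s = 17 (the plan's soybean-oil mean):
- 20% vs 10% deaths, d = 9 in both: 0.20 × (−8) − 0.10 × (−8) = −0.8 day. At d = 13 it is −0.4, at d = 17 it is 0, at d = 21 it is +0.4.
- 10% deaths in both, d = 9 vs 17: 0.10 × (−8) − 0 = −0.8 day. At 15% deaths it is −1.2.
- Equal p and equal d: 0.

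So −0.8 day is 40% of the 2-day planning difference, with no difference between survivors. The bias vanishes when p and d are both alike, or when d resembles s.

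**Effect on the test.** Simulation: gamma-distributed stays rounded up to whole days, 150 per group, survivors identical (mean 17, SD 8), two-sided 0.05. Death rates and timing are assumptions. Entries are the percentage of trials significantly favouring group A (nominal 2.5%). The last column adds the condition that the comparison of overall mortality is not significant.

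| Mortality A vs B | Decedents' mean stay A vs B | t-test | Mann-Whitney | Mann-Whitney, mortality not significant |
|---|---|---|---|---|
| 20% vs 10% | 9 vs 9 | 13.2 | 15.5 | 2.0 |
| 20% vs 10% | 13 vs 13 | 6.2 | 6.8 | 1.5 |
| 20% vs 10% | 17 vs 17 | 2.7 | 2.4 | 0.8 |
| 20% vs 10% | 21 vs 21 | 0.8 | 0.8 | 0.4 |
| 15% vs 10% | 9 vs 9 | – | 6.8 | 3.3 |
| 10% vs 10% | 9 vs 17 | 13.6 | 15.6 | 14.7 |
| 15% vs 15% | 9 vs 17 | 25.1 | 29.3 | 28.0 |
| 10% vs 10% | 9 vs 13 | – | 6.4 | – |
| 15% vs 15% | 9 vs 13 | – | 10.5 | – |

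A gap of 13 vs 17 days gives 7.0% and 10.3% at 10% and 15% mortality. Equal mortality with like stays (9 days in both) gives 2.4 to 3.0%. A lognormal model with deaths halving the stay gives 15% (t-test) and 19 to 20% (Mann-Whitney) at 20% vs 10%, so the pattern does not hang on the gamma shape.

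**The same trials with deaths ranked worst.** The chance of favouring group A is at most 0.05% at 20% vs 10%, 0.3 to 0.4% at 15% vs 10%, and 2.3 to 2.8% at equal mortality with 9 vs 17 days.

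**Power of the alternatives.** Survivors average 15 vs 17 days, mortality is equal, and decedents average 9 days in both groups.

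| SDs | Mortality | t-test | Mann-Whitney | Worst-rank | Competing-event |
|---|---|---|---|---|---|
| 6.67 both | 5% | 69 | 74 | 70 | 40 |
| 6.67 both | 10% | 62 | 67 | 60 | 29 |
| 6.67 both | 20% | 51 | 54 | 43 | 17 |
| 5 and 8 | 5% | 68 | 35 | 36 | 51 |
| 5 and 8 | 10% | 62 | 30 | 29 | 33 |
| 5 and 8 | 20% | 51 | 20 | 21 | 15 |

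**The case against.** **Mortality is reported separately.** This has force when death rates differ. At 20% vs 10%, a stay advantage for the higher-mortality group with a non-significant mortality test occurs in only 2.0% of trials, and at 15% vs 10% in 3.3%. It has much less force when rates match and deaths come earlier in one group. A reader might infer that the plan then gives no warning at all, but that is too strong. Mortality during PN is also recorded. Taking death by day 10 as a stand-in (an assumption), it differs significantly in 39% of trials at 10% mortality and 62% at 15%, for decedents at 9 vs 17 days. That is a partial warning, and the Statistical analysis section names no separate test of it.

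**Total stay is a legitimate resource-use measure.** It is, and the Introduction names costs among the things to be assessed. That supports keeping total stay if the sponsor wants it for that purpose. It does not support reading a shorter stay as clinical benefit without checking the deaths.

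**A death-aware analysis changes the question.** This stands in part. With identical survivors and 20% vs 10% deaths, worst-rank declares the lower-mortality group better in about 32% of trials and the competing-event test in about 57%.

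**Leaving deaths out is simpler.** That would compare survivors selected after allocation and does not solve the problem.

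**Conclusion.** The gap in the text is certain; the size and sign of any bias are not. The large figures (16% and 29%) need equal mortality and an 8-day gap between the groups' decedents; a 4-day gap gives 6 to 7% and 10%. The 15% figure needs mortality to double and decedents to leave about 8 days before survivors. That is the strong end of the range, since patients are expected to need PN for at least 5 days.

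Three stronger readings are not supported:
- That the plan fails to record who died. It records in-hospital death; what it lacks is a rule for using that information in the primary test.
- That the comparison is unbiased only if death rates and decedents' stays both match. Unequal rates do no harm if decedents stay about as long as survivors (the 17-day row).
- That the trial will favour the more harmful lipid. With long-staying decedents the bias runs the other way.

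This should be fixed: it touches the primary outcome and the repair uses data already collected.

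**What to change.** In Statistical analysis, Part B, before data are seen, specify a Mann-Whitney test of length of stay in which all in-hospital deaths share a rank worse than any observed stay. Then choose one of two uses:
- make it the primary analysis; or
- if total stay is kept as a resource-use measure, make it a required sensitivity analysis, and do not interpret a shorter stay as benefit unless it agrees.

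As support, report time to discharge alive with death as a competing event (cumulative incidence, Gray's test), and describe stays separately for survivors and decedents. Apply the same principle to days in ICU and antibiotic-days, which death also cuts short.

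Cost: a change of analysis text, with no new data and no request for more patients. The worst-rank result is partly driven by mortality and is not a difference in mean days. If it becomes primary, the power statement in Feasibility and Sample Size must be restated. With a 2-day survivor gap, 10% mortality and a common SD of 6.67, worst-rank loses about 7 percentage points against plain Mann-Whitney and 2 against the t-test. At SDs of 5 and 8 it matches plain Mann-Whitney, and both fall far below the t-test. There the loss comes from using ranks, which the plan already allows. The competing-event test suits a supporting role better, because its power falls steeply as mortality rises under either SD assumption.

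### The primary length-of-stay test is left to the data, and the stated 80% power holds for neither candidate: about 73.5% for the comparison of means, and roughly 34% to 86% for Mann-Whitney if stay is skewed

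*Combined protocol and SAP*

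**What the plan says.** Under Statistical analysis, Part B, the plan states that for the lipid comparison "all variables will be tested for normal distribution (Shapiro Wilks test"). It then names length of stay in days as the primary outcome and continues: "The Intralipid and ClinOleic groups will initially be compared with unpaired t-test or Mann-Whitney test as appropriate". Regression with covariates is to follow, but no model is fixed and none is given a primary role. On error rates: "All tests will be based on two-sided alternatives and a test will be considered statistically significant using alpha=0.05".

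Under Feasibility and Sample Size, Part B, the planning figures come from a cited trial of soybean oil with and without fish oil after cancer surgery: "Mean (SD) 15(5) versus 17(8) p= 0.041". On detecting a gap of about that size, the plan concludes: "we estimate that a sample size of 150 in each group with a power of 0.8 and alpha of 0.05 will be sufficient". It cites an online t-test calculator. It does not give the SD entered, a distribution for length of stay, or any power for Mann-Whitney.

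**The concern.** The trial is sized on one quantity, a difference of 2 days in mean stay, but may be judged on another. A t-test compares means. Mann-Whitney asks whether a stay in one arm tends to exceed a stay in the other. Which of the two carries the primary conclusion is settled only after the data are seen, and no selection rule is written down.

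Hospital stay cannot be negative, and a mean of 17 with SD 8 puts zero only 17/8 = 2.1 SDs below the mean. The study also mixes medical, surgical and ICU patients. Skew is therefore likely, and at 150 per arm a normality test will usually detect it. The stated power would then belong to a test that is not run. At stake are the power of the main comparison and the meaning of its result.

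**Working it through.** **Inputs.** Means 15 and 17, SDs 5 and 8, 150 per arm, 1:1 allocation, two-sided alpha 0.05, stated power 0.80 (Statistical analysis; Feasibility and Sample Size). Dropout is not stated and is taken as zero.

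**Step 1: the plan's own figure.** Pooled SD = √((25 + 64)/2) = 6.67. The normal approximation gives power = Φ(2/(6.67 × √(2/150)) − 1.96) = Φ(2.597 − 1.96) = 0.738; the noncentral t gives 0.735. For 80% power, n per arm = 2 × (1.96 + 0.8416)² × 44.5/2² = 174.6, so 175 (176 by noncentral t). The stated 80% is not reproduced. The variants tried were:

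| SD assumed | n per arm for 80% | Power at 150 |
|---|---|---|
| 5 | 99 | 0.93 |
| 6 | 142 | 0.82 |
| 6.18 | 150 | 0.80 |
| 6.5 | 166 | 0.76 |
| 6.67 | 175 | 0.74 |
| 8 | 252 | 0.58 |
| 6.67, one-sided | 138 | 0.83 |

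Only an SD near 6.18 returns 150, and the documents do not give that value. The one-sided row is excluded by the plan's two-sided rule.

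**Step 2: Mann-Whitney, one case by formula.** Means and SDs do not fix the power of a rank test, so a shape must be assumed. For a lognormal with the quoted means and SDs:

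- Log variances: ln(1 + (5/15)²) = 0.1054 and ln(1 + (8/17)²) = 0.2000.
- Log means: ln 15 − 0.0527 = 2.655 and ln 17 − 0.1000 = 2.733. The medians are 14.2 and 15.4 days, only 1.15 apart.
- P(X < Y) = Φ((2.733 − 2.655)/√0.3054) = 0.556.
- Standard error = √(301/(12 × 150²)) = 0.0334.
- Power = Φ(0.056/0.0334 − 1.96) = 0.39.
- For 80% power, n per arm = 2.8016²/(6 × 0.056²), about 417.

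**Step 3: simulation.** There were 6,000 runs per scenario with 150 per arm. The working rule was Mann-Whitney if Shapiro-Wilk gave p < 0.05 in either arm, otherwise the t-test.

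| Scenario, 15 vs 17 days | Shapiro-Wilk rejects | Mann-Whitney | t-test | Two-stage rule |
|---|---|---|---|---|
| Normal, SD 5 vs 8 | 9.5% | 0.70 | 0.72 | 0.72 |
| Lognormal, SD 5 vs 8 | 100% | 0.39 | 0.75 | 0.39 |
| Gamma, SD 5 vs 8 | 99.9% | 0.42 | 0.75 | 0.42 |
| Weibull, SD 5 vs 8 | 78% | 0.48 | 0.75 | 0.51 |
| Lognormal shifted 5 days, SD 5 vs 8 | 100% | 0.40 | 0.75 | 0.40 |
| Gamma shifted 5 days, SD 5 vs 8 | 100% | 0.34 | 0.76 | 0.34 |
| Lognormal, common CV | 100% | 0.74 | 0.73 | 0.74 |
| Gamma, common CV | 99.9% | 0.70 | 0.73 | 0.70 |
| Lognormal, common SD 6.67 | 100% | 0.85 | 0.73 | 0.85 |
| Gamma, common SD 6.67 | 99.9% | 0.79 | 0.73 | 0.79 |
| Lognormal, pure 2-day shift, SD 6.67 | 100% | 0.86 | 0.74 | 0.86 |

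Whole-day rounding leaves the lognormal result at 0.39. Further runs of 4,000 with whole days gave Mann-Whitney 0.68–0.75 with a common CV, and 0.64–0.67 with SDs 6 and 7.3.

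**Step 4: what each test answers.** With equal means of 16 days and SDs 5 versus 8, Mann-Whitney rejects in about 17–29% of skewed samples (gamma at the lower end, lognormal at the upper) and the t-test in about 5%. With identical distributions in the two arms, both reject at about 5%.

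**The case against.** A reader might infer that the trial has about 40% power under its own means and SDs. The documents do not support that. They give no shape for length of stay, and the low figures need skew and the 5-versus-8 split together. That split is one cited trial's sample estimate, in post-surgical cancer patients given a fish-oil comparison. This plan commits only to "will be sufficient to show a similar difference in length of stay between the two groups". With skew and a common SD, Mann-Whitney matches or beats the t-test. This part of the objection stands, so the power must be given as a range.

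A reader might also infer that Mann-Whitney inflates the type I error. It does not when the emulsions leave the distribution of stay unchanged. The 17–29% arises because the two distributions differ in spread, so it reflects a different estimand.

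The link from Shapiro-Wilk to the choice of test is inferred from adjacent sentences. No level or per-arm rule is given, so the rule used in the simulation is a construction. It remains the natural reading, since the normality test has no other stated use; without it, the choice has no rule at all.

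Finally, a pre-specified rank test is a respectable choice for skewed stay, and nothing in the documents compels a comparison of means. That is true, but the plan neither pre-specifies the rank test nor sizes the trial for it. The later covariate regression does not fill the gap, because it is not the named primary analysis.

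**Conclusion.** The point holds in this form: no single primary test or effect measure is fixed for length of stay, and the stated 80% is not delivered by either candidate on the plan's figures. The comparison of means falls short by about 6 points (80% to about 73.5%). That part is sample-size arithmetic and needs no assumption about shape. It does depend on the SDs: a common SD of 8 would give 58%.

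The Mann-Whitney path rests on assumed skew. Its power is then about 34–48% with SDs 5 versus 8, 68–75% with a common CV, and 79–86% with a common SD of 6.67. Any loss due to the choice of test should be measured from about 74%, not from 80%. It comes from skew combined with unequal spread, and not from the rank test as such.

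**What to change.** Remove the normality gate for length of stay and name one primary test and effect measure before any data are seen. The choice consistent with the sample-size basis is the difference in mean days with a Welch or robust standard error and a 95% CI, whatever the distribution. Keep Mann-Whitney as a labelled supportive analysis. Restate the power as about 73–74% at 150 per arm, with the assumed difference and SDs written out; about 176 per arm would be needed to keep 80%. If the sponsor prefers the rank test as primary, its power should be recomputed with a stated shape and stated SDs.

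The cost is a change of wording and a slightly less favourable stated power. One real trade-off remains: if the arms prove skewed with similar SDs, the comparison of means gives up some power relative to Mann-Whitney (about 73–74% against 79–86% in the common-SD runs).
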